1. ABBREVIATIONS

Atrial Fibrillation AF

Mitral Valvular Surgery MVS

Radiofrequency ablation RFA

Transthoracic Doppler Echocardiography TDE

Electrocardiogram ECG

2. STUDY SUMMARY

Title	A New Operation (Left Atrial Geometric Volume Reduction, Pulmonary Vein Island Isolation and Left Appendage Base Closure) for the Treatment of Long Standing Persistent Atrial Fibrillation (AF) During Mitral Valve Surgery
Objectives	Phase I: To examine the feasibility of our new operation (left atrial geometric volume reduction, pulmonary vein island isolation and left appendage base closure) based on a new concept for AF elimination Phase II: To assess the safety and efficacy of the new operation for the treatment of long-standing persistent AF during mitral valve surgery
Protocol Number	NCT 03347695
Study Design	Phase I: Prospective, single-arm pilot study Phase II: Prospective, single-arm clinical trial
Study Duration	3 years, (Phase I: from 2017 to 2018; Phase II: from 2018 to 2020)
Study Center	Fujian Medical University Union Hospital
Study Population	Adult patients with long-standing persistent AF had clinical indications for mitral valvular surgery (MVS)
Sample Size	The study will enroll a maximum of 140 patients. Phase I: 20 patients with longstanding persistent AF. Phase II: 120 patients with longstanding persistent AF.
Intervention	Evaluation: Transthoracic 2-dimensional echocardiography and Holter Operation: new operation (left atrial geometric volume reduction, pulmonary vein island isolation and left appendage base closure) Routine postoperative management: receiving amiodarone beginning within 24 hours post-operation until the 3-month point.
Primary endpoints	Efficacy: freedom from AF at both 6 months and 12 months after surgery, assessed by 7-days continuous Holter monitoring. Safety: cardiopulmonary bypass time; and a composite of death, stroke, serious cardiac events (heart failure, myocardial infarction), cardiac re-hospitalizations, transient ischemic attack, pulmonary embolism, peripheral embolism, coronary artery injury, anatomical excessive bleeding, deep sternal wound infection/mediastinitis, damage to specialized conduction system requiring permanent pacemaker, and superior vena cava stenosis, within 30 days after the procedure or hospital discharge (whichever was later)
Secondary endpoints	Efficacy: The left atrial linear dimensions and A wave reappearance measured by transthoracic echocardiography at 3 time points (before surgery, 6 and 12 months after surgery).

	
Safety: Major adverse cardiac events, which were defined as a non-weighted composite score of: death, stroke, worsening heart failure (+1 NYHA Class), hospitalization for heart failure, and mitral valve re-intervention within 12 months after surgery; and incidence of protocol-defined serious adverse events (especially thromboembolic and hemorrhagic events) within 12 months after surgery.

Follow-up Schedule	
Pre-discharge, and at 30 days, 3, 6, and 12 months after surgery.

3. BACKGROUND

Atrial fibrillation (AF) often occurs in patients with valvular disease, especially in those with mitral valve disease, leading to an elevated mortality.¹ Though valvular replacement and plasty are the effective methods to treat valve disease, valvular procedure alone is not enough to cure AF.^{2,3} AF can cause thromboembolism and stroke in approximately 5 -10% of high-risk patients, the risk of which increases with age and the coexistence of structural heart disease.³⁻⁵

The cut-and-sew Cox-Maze III operation, developed in 1989, has been regarded as the golden standard surgery for AF elimination.⁶ In this surgical procedure, the atrial wall is divided into small areas to electrically isolate from each other, which is then not large enough to sustain the macro-reentry circuits. While it has not been widely used because it is complex and time-consuming, and the incisions are risky in both atria. Another procedure, known as Cox-Maze IV, was then developed and broadly accepted as the preferred technique for AF elimination, in which the classic cut and sew lesions are replaced with ablative lines using various energy sources. However, completion of so many ablative lines is still time-consuming.⁵

AF is always accompanied with an enlarged left atrium. Volume reduction of the enlarged atrium can decrease operative morbidity and incidence of AF recurrence after simultaneous mitral and AF surgery.⁷ Unfortunately, the additional left atrial volume reduction was rarely performed because it will further prolong the aortic cross-clamp time. In both analogous Cox-Maze III and IV, the division of the entire intact atria into small areas has been proven to negatively affect the restoration of atrial transport function after appearance of sinus rhythm.⁸⁻¹⁰ Therefore, it is desirable to develop a simple AF elimination technique which will benefit both atrial appropriate volume restoration and transport function reappearance.

In a cross-sectional study, we found the left atrial spatial enlargement and the fibrosis regional distribution were not uniform. We thus proposed a new concept that reconstructing a new left atrium with appropriate size and shape and a uniform fibrosis distribution for conduction is effective for AF elimination. Based on this concept, a new procedure (left atrial geometric volume reduction, pulmonary veins island isolation and left appendage base closure), was developed to render left atrium appropriate geometry and achieve uniform fibrosis distribution. Therefore, we conduct this proof-of-concept study to determine the feasibility, efficacy and safety of the new procedure.

4. OBJECTIVES

Primary objective

The primary objective is to assess the efficacy and safety of the new procedure (left atrial geometric volume reduction, pulmonary veins island isolation and left appendage base closure) for treating long standing persistent AF elimination. Efficacy will be evaluated by freedom from AF within 6 months and 12 months after surgery. Safety will be assessed by a composite of early adverse outcomes (within 30 days post-procedure or hospital discharge, whichever is later), including death, stroke, serious cardiac events (heart failure, myocardial infarction), cardiac re-hospitalizations, transient ischemic attack, pulmonary embolism, peripheral embolism, coronary artery injury, anatomical excessive bleeding, deep sternal wound infection/mediastinitis, damage to specialized conduction system requiring permanent pacemaker, and superior vena cava stenosis. We hypothesize that the new procedure will reduce the risk of AF post-MVS reoccurrence and lower the incidence of adverse outcomes, as compared to that was historically reported in patients undergoing MVS concomitantly with COX MAZE IV.

Secondary objectives

- (a) To assess the incidence of major adverse cardiac events and protocol-defined and serious adverse events (especially thromboembolic and hemorrhagic events) within 12 months after surgery, which is hypothesized to be lower than MVS concomitantly with COX MAZE IV.
- (b) To assess the intra-operation cardiopulmonary bypass time(CPB), which if prolonged could increase risk of poor prognosis within 30 days post-procedure or hospital discharge. CPB time is hypothesized to be shorter than that historically reported in COX MAZE IV procedure.
- (c) To assess the changes of size and shape of left atrium. The post-surgical shape and size of left atrium is hypothesized to be closer to normal status.
- (d) To assess the function of left atrium. The incidence of peak late trans-mitral flow velocity (A) at 12 months post-surgery is supposed to be high.

5. STUDY DESIGN

This is a prospective, single-arm objective performance criteria study, consisting of two phases.

Phase I: A single-arm pilot study, 20 patients will be enrolled to test the feasibility of the procedure.

Phase II: A single-arm clinical trial, 120 patients will be enrolled to determine the safety and efficacy of the procedure.

Total study period is expected to take 40 months, and all patients will be followed for 12 months after surgery.

6. STUDY POPULATION

Recruitment

Patients admitted to our center will be enrolled in this study. Based on the average hospitalization admissions in our center, it is estimated that approximately 50 patients could be enrolled annually.

Characterization of Patient Population

The patient population for the pilot study is adult patients with both longstanding persistent AF and mitral valve disease requiring surgical intervention. Longstanding persistent AF is defined as continuous AF of greater than one year duration. This definition applies only to AF episodes that are of at least 30 seconds' duration and do not have a reversible cause such as acute pulmonary disease or hyperthyroidism. All patients who meet the eligibility criteria will be included in the study regardless of gender, race or ethnicity.

Phase I

Inclusion Criteria

1. Able to sign Informed Consent and Release of Medical Information forms
2. Age \geq 18 years and \leq 60 years old
3. Clinical indications for only mitral valve surgery for the following:
 - Organic mitral valve disease without other cardiac disorders (functional or structural).
4. Longstanding persistent AF is defined as continuous AF of greater than one year duration.
 - Duration of AF must be documented by medical history and
 - Presence of AF must be documented by a direct electrocardiographic assessment upon arrival in the clinic.
5. Able to use heart rhythm monitor
6. Anteroposterior diameter of left atrial between 45mm and 60mm
7. Without history of stroke.

Exclusion Criteria

1. AF without indication for mitral valve surgery; or
2. Ischemic mitral regurgitation with evidence of concomitant structural mitral valve disease; or

3. Functional tricuspid regurgitation; or
4. AF is only or paroxysmal persistent; or
5. Evidence of active infection; or
6. Mental impairment or other conditions that may not allow patient to understand the nature, significance, and scope of study; or
7. Surgical management of hypertrophic obstructive cardiomyopathy; or
8. Previous catheter ablation for AF; or
9. Life expectancy of less than one year; or
10. Absolute contraindications for anticoagulation therapy; or
11. Enrollment in concomitant drug or device trials; or
12. Uncontrolled hypo- or hyperthyroidism; or
13. FEV1 < 30% of predicted value; or
14. Women who are pregnant as evidenced by positive pregnancy test; or
15. Women of childbearing age who do not agree to be on adequate birth control throughout the period of the trial; or
16. Diagnosed with infective endocarditis; or
17. Need emergency surgery.

Phase II

Inclusion Criteria

1. Able to sign Informed Consent and Release of Medical Information forms
2. Age \geq 18 years
3. Clinical indications for mitral valve surgery for the following:
 - Organic mitral valve disease; or
 - Functional non-ischemic mitral regurgitation; or
 - Ischemic mitral regurgitation with evidence of concomitant structural mitral valve disease.

Note: May include need for surgical management of functional tricuspid regurgitation or patent foramen ovale. May also include concomitant CABG, aortic arch or aortic valve procedure. Surgical intervention may be performed via sternotomy or minimally invasive procedure.

4. Longstanding persistent AF is defined as continuous AF of greater than one year duration.

Duration of AF must be documented by medical history and

Presence of AF must be documented by a direct electrocardiographic assessment upon arrival in the clinic.

5. Able to use heart rhythm monitor

Exclusion Criteria

1. AF without indication for mitral valve surgery; or
2. AF is only or paroxysmal persistent; or
3. Evidence of active infection; or
4. Mental impairment or other conditions that may not allow patient to understand the nature, significance, and scope of study; or
5. Surgical management of hypertrophic obstructive cardiomyopathy; or
6. Previous catheter ablation for AF; or
7. Life expectancy of less than one year; or
8. Absolute contraindications for anticoagulation therapy; or
9. Enrollment in concomitant drug or device trials; or
10. Uncontrolled hypo- or hyperthyroidism; or
11. Women who are pregnant as evidenced by positive pregnancy test; or
12. Women of childbearing age who do not agree to be on adequate birth control throughout the period of the trial; or
13. Diagnosed with infective endocarditis; or
14. Need emergency surgery.

7. INTERVENTIONS

The new procedure

All patients will have their left atrial geometric volume reduced, pulmonary vein island isolated and left appendage ligated or suture closed. After the superior vena cava was transected, two circular incisions were usually made in the left atrial wall between the pulmonary veins and the mitral annulus for circumferential atrial strip resection and pulmonary vein island isolation. The first circular incision was performed around the pulmonary veins. With this incision, pulmonary vein island was isolated and the left atrium was opened. The second one was performed in the interatrial groove and extended around the mitral annulus, leaving a 2 cm inferior wall margin from the annulus and the appendage in situ. With those two incisions, a circumferential strip of the left atrium was excised. Then the base of the left atrial appendage was ligated or excised and sutured. After the mitral manipulations, the center of the pulmonary vein island was longitudinally reef-imbricated with a 3-0 polypropylene continuous running suture to exclude toward the outside of the left atrial cavity. This plicated pulmonary vein island was directly anastomosed to the resected margin around the mitral annulus and the intraatrial septum instead of the interatrial groove. Finally, caval continuity was restored after aortic cross-clamp removal using a running 4-0 polypropylene suture.

Mitral Valve Surgery

For mitral regurgitation, the procedures will be a valve repair in the majority of cases. For valves that are not amenable to repair, and for most cases of mitral stenosis, a valve replacement will be performed. And the cardiopulmonary bypass time will be recorded.

Transthoracic Doppler Echocardiography

Transthoracic Doppler Echocardiography(TDE) will be used to measure left atrial size and volumes, quantify mitral valve function, detect intracardiac thrombi, and to assess left atrial and left ventricular function. TDE will be used to measure LA size as well as diameters in LA.

Electrocardiogram (ECG)

An ECG will be done upon arrival in the operating room. This tracing will be used to assess heart rhythm on all patients and provide part of the documentation needed to establish the diagnosis of longstanding persistent AF.

Postoperative management

Standardization of Anti-arrhythmic Drug Use during Follow-up

Unless contraindicated (hypotension or bradycardia defined as heart rate less than 60 beats per minute), all patients will receive prophylactic amiodarone beginning within 24 hours post-operation. Patients will be discharged on the anti-arrhythmic agent. At the 3-month point, antiarrhythmic agents will be terminated in all patients and this recommendation communicated by study personnel to the managing physician. Direct current cardioversion will be performed as clinically indicated by managing physicians and recorded by study personnel for the duration of follow-up.

Anticoagulation

Unless specifically contraindicated, warfarin will be prescribed for all patients at hospital discharge, with a target INR of 2.0-2.5. It is recommended that warfarin be continued in patients for the entire duration of the study if in mechanical valve replacement status or AF was detected at follow-up time points.

8. ENDPOINTS

Primary Endpoints

Efficacy

Freedom from AF in patients with longstanding persistent AF undergoing MVS at 6 months and 12 months. AF will be measured by 7 days continuous Holter monitoring at 6 months and 12 months post-surgery; and freedom of AF will be defined by absence of AF lasting > 30 seconds at 12 months.

Patients will be considered as treatment failures (not free of AF) if: 1) they die prior to the 12-month assessment; 2) or they are determined by an independent adjudicator to be too ill to undergo AF assessment; 3) or they require additional ablation therapy for AF (including surgical ablation or percutaneous catheter ablation) subsequent to the index procedure.

Safety

(a)Cardiopulmonary bypass time, which if prolonged could increase risk of poor prognosis within 30 days post-procedure or hospital discharge;

(b)The adverse events within 30 days after surgery, including: death, stroke, serious cardiac events (heart failure, myocardial infarction), cardiac re-hospitalizations, transient ischemic attack, pulmonary embolism, peripheral embolism, coronary artery injury, anatomical excessive bleeding, deep sternal wound infection/mediastinitis, damage to specialized conduction system requiring permanent pacemaker, and superior vena cava stenosis.

Secondary Endpoints

Efficacy

(a)The changes of size and shape of left atrium, which will be measured by comparing the anteroposterior, transversal, and superoinferior diameters of left atrium between 3 time points (i.e., before surgery, 6 months and 12 months post-surgery) by using transthoracic echocardiography.

(b)The peak late trans-mitral flow velocity (A) at 6 months and 12 months post-surgery, which will be measured by transthoracic echocardiography.

Safety

(a)MACEs within 12 months after surgery: defined as a non-weighted composite score

of: death, stroke, worsening heart failure (+1 NYHA Class), CHF hospitalization, and mitral valve [MV] re-intervention.

(b) Protocol-defined and serious cerebrovascular adverse events (especially thromboembolic and hemorrhagic events) within 12 months after surgery.

(c) All-cause mortality at 12 months after surgery.

9. DATA COLLECTION

Data collected at hospital admission

Demographics

A screened patient is defined as an individual (a consented patient) who was referred to, or identified at a clinical site for consideration of entry into the study, and for whom some preliminary (i.e. medical record) data have been collected and/or reviewed. For all patients screened, the first, middle, and last initial, date of birth, ethnic origin, and sex will be captured on the screening log and registration form. The EDC will generate a unique 8-digit identification code that will identify the patient throughout the course of the study.

Medical History

Within 30 days prior to surgery

This form captures the information pertaining to the medical history, including but not limited to previous myocardial infarction, myocardial revascularization, arrhythmias, automatic implantable cardioverter-defibrillator, permanent right ventricular or biventricular pacemaker, stroke and other comorbidities such as diabetes and peripheral vascular disease. Information regarding the current medical condition is also captured, including but not limited to disposition at time of screening (outpatient, inpatient, ICU monitoring, etc) and intra-aortic balloon pump use.

Medications

Within 30 days prior to surgery

This form captures all protocol-defined medications taken within 7 days prior to surgery.

Physical Examination

Within 30 days prior to surgery

This form captures the comprehensive physical examination including vital signs cardiopulmonary examination, abdominal examination, and anthropometrics (height, weight and BSA).

Laboratory Assessment

Within 30 days prior to randomization

- White blood cell ($10^3/\mu\text{L}$)
- Hemoglobin (g/dL)
- Hematocrit (%)
- Platelet count ($10^3/\mu\text{L}$)

- Prothrombin time (PT/sec), partial thromboplastin time (PTT/sec)
- International Normalized Ratio (INR)
- Blood chemistries, including sodium (mM/L), potassium (mM/L), blood urea nitrogen (mg/dL), creatinine (mg/dL).
- Liver function tests, including total bilirubin (mg/dL), alanine aminotransferase (ALT U/L), aspartate aminotransferase AST (U/L), albumin (g/dL), lactate dehydrogenase (LDH).
- Urine or serum beta HCG (IU/L) is required for women who have the potential to
- become pregnant

Cardiovascular Rhythm Assessment

Prior to surgery

Physicians must document in the Medical History Form the timing and duration of AF. An ECG or other direct assessment of heart rhythm will be obtained within 1 year prior to document the presence of long-standing persistent AF. All long-standing persistent AF patients will undergo an ECG upon arrival in the operating room (OR). Furthermore, there will be a baseline transthoracic Doppler echocardiogram performed within 3 months prior to surgery.

Data collected during hospitalization

Informed consent

A detailed explanation of the risks and benefits of the study will be outlined by the investigator to each patient or their legally authorized representative before any preoperative assessments that are not part of the routine preparation and they will be asked to sign a consent form.

Surgical Procedures

Initial surgical intervention and event driven

Includes information regarding specific primary procedure, operative variables, lesion sets created, additional procedures performed at time of initial operation, intra-operative pharmacological agents, intra-operative blood transfusions, the cardiopulmonary bypass time.

Medications

All cardiovascular medications are recorded, including amiodarone given prophylactically since surgery.

Physical Examination (including vital signs and cardiopulmonary examination)

Electrocardiogram (12-lead ECG)

Adverse Events

Detailed information regarding adverse events is recorded at the time an event occurs during hospitalization. Investigators are asked to make a judgment as to the seriousness and relationship of the event to the surgical intervention.

Patient Discharge

Patients clinically stable for discharge may be discharged to an affiliated rehabilitation center, intermediate care center, long-term care facility, step-down facility or home.

Data collected at follow-up

Follow-up visits will be conducted at 30 days, 3 months, 6 months and 12 months after surgery (± 30 days) after surgery provided that the patient is still alive. The following assessments are scheduled at each visit:

Transthoracic Doppler Echocardiogram

All patients will undergo follow-up transthoracic Doppler echocardiography at the investigative center*. Transthoracic Doppler echocardiography will be used to measure LA function (a) atrial filling, (b) LA ejection fraction, (c) atrial systolic mitral annular velocity (TDI). MV function, mitral regurgitation and LV function will be measured.

24-hour Holter Monitoring

The 24-hour holter monitoring provided to patients will be used for this assessment.

Medications

All cardiovascular, inotropic, antiplatelet agents, and anticoagulants will be recorded. Medications (including AADs) will be recorded at the study visit, and also as indicated at the time of associated adverse events. Response to DC cardioversions (success or failure) will also be recorded.

Functional Status

NYHA classification will be determined by a coordinator or physician not otherwise involved in this trial and blinded to the treatment assignment. The NYHA class will be documented on the "New York Heart Association Classification" form.

Adverse Events, Anti-arrhythmic Interventions, and Hospitalizations

Patients will be asked to recall any adverse events (including stroke and bleeding) and the number of hospitalizations that occurred out of network since the last contact. Patients will also be asked if they had a permanent pacemaker insertion, cardioversion or subsequent ablation since the last contact.

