12. ANALYTICAL PLAN

Statistical overview

The aim of this study is to assess the safety and efficacy of our new operation (left atrial geometric volume reduction, pulmonary vein island isolation and left appendage base closure) in patients with MV disease and longstanding persistent AF. This study included a pilot study and a clinical trial, both of which are prospective, single-arm studies with similar statistical analysis plan.

Sample size

Sample size is based on previously published data, and on ensuring the ability to detect, with high probability, a clinically meaningful presumed benefit for our new operation. To date there have been some studies examining effect of COX MAZE IV in treating AF in MVS patients. The reported absence of AF one year post MVS with COX MAZE IV is about 60%-80%. For computing sample size, according to our pilot study, a reasonable proportion of patients free from AF at 1 year, will be assumed.

As observed in the pilot study that 20/20 (100%) patients free from AF at 6-month follow-up, we assume that 90% of patients treated with our new operation will be free of AF at 1-year post-surgery. A total of 120 patients enrolled in the clinical trial provides 80% power to detect an absolute increase of 10% (80% versus 90%) in the proportion of patients free of AF, based on a single-tailed 0.025 level continuity corrected chi-squared test and 10% drop-out rate. (ADDED at August 2018)

Primary analysis

The primary outcome of efficacy is freedom from AF over one year post surgery. The rate of free of AF will be calculated after finishing 1-year follow-up for 120 patients. Patients who die within 12 months will be considered treatment failures (not free of AF). Patients who die prior to the 12-month assessment, or who are determined by an independent adjudicator to be too ill to undergo AF measurement, will be considered as treatment failures (not free of AF). In the primary analysis, patients who undergo ablation therapy for AF (including surgical ablation or percutaneous catheter ablation) subsequent to the index procedure will be considered treatment failures (not free of AF). The primary safety endpoint of this trial include:

- (a) CPB time will be recorded.
- (b) a composite of death, stroke, serious cardiac events (heart failure, myocardial infarction), cardiac re-hospitalizations, transient ischemic attack, pulmonary embolism,

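### The primary efficacy endpoint is defined by a 7-day Holter at 6 and 12 months, but the follow-up schedule for those visits has a 24-hour Holter as its only rhythm recording

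*Combined protocol and SAP*

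**What the plan says.** Section 2 (Study Summary, primary endpoints) gives the efficacy endpoint as "freedom from AF at both 6 months and 12 months after surgery, assessed by 7-days continuous Holter monitoring". Section 8 (Endpoints, primary efficacy) agrees on device, duration and timing: "AF will be measured by 7 days continuous Holter monitoring at 6 months and 12 months post-surgery". It then sets the threshold: "freedom of AF will be defined by absence of AF lasting > 30 seconds at 12 months". Section 8 also counts three groups as failures without reference to a recording: deaths before the 12-month assessment, patients adjudicated too ill to be assessed, and patients who need further ablation.

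Section 9 (Data collected at follow-up) reads differently. It sets the visits, "Follow-up visits will be conducted at 30 days, 3 months, 6 months and 12 months after surgery", and introduces its list with "The following assessments are scheduled at each visit". The list covers echocardiography, Holter monitoring, medications, NYHA class, and adverse events with hospitalizations. The Holter item is headed as 24-hour monitoring, and its whole text is: "The 24-hour holter monitoring provided to patients will be used for this assessment". Section 9 schedules no 7-day recording.

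Section 12 (Primary analysis) says "The rate of free of AF will be calculated after finishing 1-year follow-up for 120 patients" but names neither a device nor a recording length.

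**The concern.** The section that defines the primary endpoint and the section from which visits are run ask for different recordings at the same two visits. A site could complete every item in Section 9 at 6 and 12 months and still not hold the recording that the endpoint needs. A 7-day recording that was not made at the visit cannot be recovered afterwards.

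Recording length matters because one AF episode of more than 30 seconds on the monitor makes the patient a failure. A shorter window gives fewer chances to see one. If 24 hours replaced 7 days, the AF-free rate would tend to rise, and it could not fall if the 24 hours lie within the same 7 days. If some patients had one length and some the other, the pooled rate would mix two different quantities. The trial has a single arm and its sample size is built on a fixed 80% comparator, so no concurrent control would carry the same error.

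**Working it through.** **The text.** Side by side:

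| Section | 6 months | 12 months | Recording named |
|---|---|---|---|
| 2, Study Summary | yes | yes | 7-day continuous Holter |
| 8, Endpoints | yes | yes | 7-day continuous Holter |
| 9, Data collected at follow-up | yes (every visit) | yes (every visit) | 24-hour Holter |
| 12, Primary analysis | not stated | one year | none |

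To reconcile these, the plan would have to limit the 24-hour Holter to 30 days and 3 months, call it additional to the 7-day one, or state which section prevails. It does none of these.

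**The plan's own sample size, to fix the evaluable number.** Section 12 gives 80% versus 90%, one-sided 0.025, 80% power, 10% drop-out and 120 patients.

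- One-sample formula: n = [(1.960 × √(0.8 × 0.2) + 0.842 × √(0.9 × 0.1)) / 0.10]² = 107.4, rounded up to 108.
- Drop-out: 108 / 0.90 = 120, which matches.
- This match is without the continuity correction that Section 12 names. With it, n is 118 and the total 132. That is a separate matter and does not affect this point.

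So 120 × 0.90 = 108 evaluable patients.

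**Success cutoffs at n = 108 against 80%.** The expected count is 86.4 and its standard deviation is √(108 × 0.8 × 0.2) = 4.157.

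- Continuity-corrected z = (k − 0.5 − 86.4) / 4.157. For k = 95, z = 1.949, below 1.960. For k = 96, z = 2.189. The cutoff is 96.
- Exact binomial: P(X ≥ 94) = 0.0388 and P(X ≥ 95) = 0.0210. The cutoff is 95.

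The primary analysis text names no test. The first cutoff follows the test named for the sample size, and the second is shown for comparison.

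**Illustration of the effect.** Two inputs are assumptions and appear nowhere in the documents: f, the number of failures not based on rhythm (death, too ill, repeat ablation), and m, the share of rhythm-detected failures that a 24-hour recording would miss. The true 7-day AF-free rate is set at 80%, so expected failures are 108 × 0.20 = 21.6. Then

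apparent rate = 0.80 + (21.6 − f) × m / 108.

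With f = 5, 16.6 failures are rhythm-detected:

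| m | Patients missed | Apparent rate | P(X ≥ 96), corrected | P(X ≥ 95), exact |
|---|---|---|---|---|
| 0 | 0 | 80.0% | 0.0105 | 0.0210 |
| 5% | 0.8 | 80.8% | 0.0171 | 0.0327 |
| 12.5% | 2.1 | 81.9% | 0.0339 | 0.0608 |
| 25% | 4.2 | 83.8% | 0.0936 | 0.1501 |

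Varying f at m = 25%:

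- f = 0: apparent rate 85.0%, false-success chance 0.1591 (corrected) or 0.2381 (exact).
- f = 10: apparent rate 82.7%, false-success chance 0.0518 (corrected) or 0.0888 (exact).

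**The case against.** The strongest reply is that this is an omission and not a contradiction. Sections 2 and 8 agree with each other and are explicit. Section 9 never says that the 24-hour recording decides the endpoint or replaces the 7-day one. Both can be done, and skipping the 7-day Holter would breach Section 8 and so count as a deviation under Section 11. Section 9 also contains other wording that does not fit a single-arm trial, such as references to randomization and to blinding to treatment assignment, which suggests carried-over text. It is fair that staff could do both. But the Section 9 list expressly covers the 6- and 12-month visits, no precedence is stated, and carried-over text still directs what is done.

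Three objections to the size also have weight:

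- The documents do not give the recording length behind the 80% comparator, which comes from published Cox-Maze IV results of about 60%-80%. If those studies used short recordings, 24 hours might be the closer comparison. The illustration takes 80% as a 7-day rate, and that is a further assumption.
- Under the continuity-corrected test with f = 5, the false-success chance stays at or below 2.5% until about 9% of rhythm failures are missed.
- The size is driven by the assumed miss share.

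These limit what the numbers can show. They do not remove the conflict over which recording is required.

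**Conclusion.** The concern holds and must be fixed. Sections 2 and 8 require a 7-day recording at visits for which Section 9 schedules only a 24-hour one among its rhythm assessments, and no text settles which applies. This rests on the wording alone and is held with high confidence.

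The consequence is certain in direction only for a 24-hour window within the same 7 days: the AF-free rate stays the same or rises. It touches rhythm-detected failures only. Its size is not known, and the illustrated range runs from no effect to a false-success chance of 16% (corrected) or 24% (exact). That range depends on the assumed miss share (0 to 25%), the assumed number of other failures (0 to 10), a true 7-day rate of 80% and 108 evaluable patients. The rating does not depend on it: the conflict determines whether the primary endpoint data are collected as defined.

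**What to change.** - Section 9: schedule the 7-day continuous Holter of Section 8 at the 6- and 12-month visits, and limit the 24-hour Holter to the 30-day and 3-month visits.
- Section 12: add a sentence naming the 7-day recording as the source for the primary analysis, and report the recorded duration for each patient so that short recordings are visible.

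The Section 9 scheduling line is the essential part. The rest closes the remaining ambiguity over which recording counts. The cost is a few words in Section 9 and a sentence in Section 12. No procedure is added, because Sections 2 and 8 already commit to the 7-day monitoring.
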